Adverse Events and Serious Adverse Events Assessment	X	X	Record at each visit. Participants will be followed for drug-related toxicities until these toxicities resolve, return to baseline, or are deemed irreversible. All adverse events will be documented for a minimum of 100 days after last dose (Appendix 3).
██████████	█	█	██████████
Electrocardiogram (ECG)	X	X (See notes)	Fridericia corrected QT (QTcF) required. Only for Cycles 1, 4, 7, then every 6 cycles (ie, Cycles 13, 19, 25, etc). If any time there is an increase in QTcF interval to an absolute value > 500 msec, 2 additional ECGs must be performed each with intervals approximately 3 minutes apart.
Laboratory Tests (includes blood and urine samples)	X	X (See notes)	See 9.4.1 for additional details on tests required. Laboratory tests do not need to be repeated at C1D1 if performed within 14 days prior to first dose. After C1D1, within 72 hours prior to dosing: 
 • CBC w/differential at every cycle • Chemistry panel at every cycle (includes AST, ALT, total bilirubin, ALP, LDH, creatinine, BUN, glucose, albumin, Na, K, Cl, Ca, P, Mg) • Amylase and lipase to be done for Cycles, 1, 2, 4, 5, 7, and then every 3 cycles (ie, Cycles 10, 13, 16, etc) • Thyroid panel (includes TSH with reflexive free T3 and free T4) for Cycles 1, 2, 4, 5, 7, and then every 3 cycles (ie, Cycles 10, 13, 16, etc) • Urine protein and urine creatinine (for UPCR, preferred) or urine dipstick for protein every 3 cycles (ie, Cycles 1, 4, 7, 10, etc).

Table 2-2: On Treatment Procedural Outline for Arm A Nivolumab Combined with Cabozantinib, Doublet (CA2099ER)

Procedure	Cycle 1, Day 1 Cycle=2 wks	C2 and subsequent visits ^a Each Cycle=2 wks	Notes
Pregnancy Test	X	X	Within 24 hours prior to the initial administration of study drug, then every 4 weeks ± 7 days. Serum or Urine. WOCBP only.
Efficacy Assessments			

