- g) Participants with favorable, intermediate and poor risk categories will be eligible for the study. To be eligible for the Intermediate and Poor-Risk cohort, at least one of the following prognostic factors as per International Metastatic RCC Database Consortium (IMDC) must be present: (See [Appendix 6](#))
- i) KPS equal to 70%
 - ii) Less than 1 year from initial diagnosis (including original localized disease if applicable) to randomization
 - iii) Hemoglobin < lower limit of normal (LLN)
 - iv) Corrected calcium concentration > 10 mg/dL
 - v) Absolute neutrophil count > ULN
 - vi) Platelet count > ULN

If none of the above factors are present, participants are only eligible for the favorable-risk cohort. Approximately 160 favorable risk participants will be randomized. Enrollment of favorable risk participants may be closed earlier than enrollment for intermediate and poor risk participants.

3) Age and Reproductive Status

- a) Males and Females, ages 18 or age of majority
- b) Women of childbearing potential (WOCBP) must have a negative serum or urine pregnancy test (minimum sensitivity 25 IU/L or equivalent units of HCG) within 24 hours prior to the start of study treatment
- c) Women must not be breastfeeding
- d) Women of childbearing potential (WOCBP) must agree to follow instructions for method(s) of contraception for the duration of study treatment and 5 months after the last dose of study treatment (ie, 30 days [duration of ovulatory cycle] plus the time required for the investigational drug to undergo approximately five half-lives).
- e) Males who are sexually active with WOCBP must agree to follow instructions for method(s) of contraception for the duration of study treatment and 7 months after the last dose of study treatment (ie, 90 days [duration of sperm turnover] plus the time required for the investigational drug to undergo approximately five half-lives).
- f) Azoospermic males are exempt from contraceptive requirements. WOCBP who are continuously not heterosexually active are also exempt from contraceptive requirements, and still must undergo pregnancy testing as described in this section.

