9.2.1 Time Period and Frequency for Collecting AE and SAE Information

The collection of nonserious AE information should begin at initiation of study treatment until the timepoints specified in the Schedule of Activities ([Section 2](#)). Nonserious AE information should also be collected from the start of a placebo lead-in period or other observational period intended to establish a baseline status for the participants.

Sections 5.6.1 and 5.6.2 in the Investigator Brochures (IBs) for Nivolumab²⁸ and Ipilimumab²⁹ represent the Reference Safety Information (also Appendix K in the IB for cabozantinib²¹) to determine expectedness of serious adverse events for expedited reporting. Following the participant's written consent to participate in the study, all SAEs, whether related or not related to study drug, must be collected, including those thought to be associated with protocol-specified procedures.

All SAEs must be collected that occur during the screening period and within 100 days of the last dose of study treatment. For participants randomized to treatment and never treated with study drug, SAEs should be collected for 30 days from the date of randomization. If applicable, SAEs must be collected that relate to any later protocol-specified procedure (eg, a follow-up skin biopsy).

The investigator must report any SAE that occurs after these time periods and that is believed to be related to study drug or protocol-specified procedure.

- Medical occurrences that begin before the start of study treatment but after obtaining informed consent will be recorded on the appropriate section of the eCRF section.
- All SAEs will be recorded and reported to Sponsor or designee within 24 hours, as indicated in [Appendix 3](#).
- The investigator will submit any updated SAE data to the sponsor within 24 hours of this being available.

Investigators are not obligated to actively seek AEs or SAEs in former study participants. However, if the investigator learns of any SAE, including a death, at any time after a participant has been discharged from the study, and he/she considers the event reasonably related to the study treatment or study participation, the investigator must promptly notify the sponsor.

The method of evaluating, and assessing causality of AEs and SAEs and the procedures for completing and reporting/transmitting SAE reports are provided in [Appendix 3](#).

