6 STUDY PERIODS, TREATMENT REGIMENS AND POPULATIONS FOR ANALYSES

6.1 Study Periods

- Baseline period:
 - Baseline evaluations or events will be defined as evaluations or events that occur before the date and time of the first dose of study treatment. Evaluations (laboratory tests, pulse oximetry and vital signs) on the same date and time of the first dose of study treatment will be considered as baseline evaluations. Events (AEs) on the same date and time of the first dose of study treatment will not be considered as pre-treatment events.
 - In cases where the time (onset time of event or evaluation time and dosing time) is missing or not collected, the following definitions will apply:
 - ◆ Pre-treatment AEs will be defined as AEs with an onset date prior to but not including the day of the first dose of study treatment;
 - ◆ Baseline evaluations (laboratory tests, pulse oximetry and vital signs) will be defined as evaluations with a date on or prior to the day of first dose of study treatment.
 - If there are multiple valid assessments on or prior to the first dose of study treatment:
 - ◆ For laboratory tests, the latest non missing labs value on or before first dose date (and time if collected) will be used as the baseline in the analyses. For 'LIPASE' and 'GLUCOSE', for treated subjects only, the last predose assessment with non-missing toxicity grade will be considered as baseline. If multiple assessments exist with the same collection date (and time if collected) and entry date and time, then the first observation is used as baseline.

- Post baseline period:
 - On-treatment AEs will be defined as AEs with an onset date and time on or after the date and time of the first dose of study treatment (or with an onset date on or after the day of first dose of study treatment if time is not collected or is missing). For subjects who are off study treatment, AEs will be included if event occurred within a safety window of 30 days (or 100 days depending on the analysis) after the last dose of study treatment. No “subtracting rule” will be applied when an AE occurs both pre-treatment and post-treatment with the same preferred term and grade.

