7.6.2 Serious Adverse Events

Serious adverse events will be summarized by treatment group:

- Overall summary of SAEs by worst CTC grade (any grade, grade 3-4, grade 5) presented by SOC/PT.
- Overall summary of drug-related SAEs by worst CTC grade (any grade, grade 3-4, grade 5) presented by SOC/PT.

All analyses will be conducted using the 30-day safety window.

A by-subject SAE listing will be provided for the “enrolled subjects” population.

Note that for all intermediate/poor risk treated subjects in Arm A and Arm C, serious adverse events will be summarized by treatment group.

Similar tables will be presented for those subjects treated in Arm B.

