7.6.3 Adverse Events Leading to Discontinuation of Study Therapy

AEs leading to discontinuation will be summarized by treatment group:

- Overall summary of AEs leading to discontinuation by worst CTC grade (any grade, grade 3-4, grade 5) presented by SOC/PT.
- Overall summary of drug-related AEs leading to discontinuation by worst CTC grade (any grade, grade 3-4, grade 5) presented by SOC/PT.

The analyses will be conducted using the 30-day safety window.

A by-subject AEs leading to discontinuation listing will be provided.

Note that for all intermediate/poor risk treated subjects in Arm A and Arm C, AEs leading to discontinuation will be summarized by treatment group.

Similar table will be presented for those subjects treated in Arm B.

Note that

- for Arm A, AEs leading to discontinuation from cabozantinib only, nivolumab only, and both cabozantinib and nivolumab.
- for Arm B, AEs leading to discontinuation from cabozantinib only, nivolumab and ipilimumab only, and from cabozantinib, nivolumab, and ipilimumab will be summarized in all the tables specified in this section.

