7.6.5 Adverse Events

Adverse events will be summarized by treatment group.

The following analyses will be conducted using the 30 days safety window only:

- Overall summary of any AEs by worst CTC grade (1, 2, 3, 4, 5, not reported, total) presented by SOC/PT.
- Overall summary of any AEs presented by worst CTC grade (any grade, grade 3-4, grade 5) by SOC/PT. This table will be restricted to events with an incidence greater or equal to 5% in any treatment group.
- Overall summary of any non-serious AEs presented by SOC/PT. This table will be restricted to events with an incidence greater or equal to 5% in any treatment group.
- Overall summary of any AEs that required immune modulating medication by worst CTC grade (any grade, grade 3-4, grade 5) presented by SOC/PT.
- Overall summary of drug-related AEs by worst CTC grade (1, 2, 3, 4, 5, not reported, total) presented by SOC/PT.

The following analyses will be conducted using the 30 days safety window and repeated using the 100 days safety window:

- Overall summary of drug-related AEs by worst CTC grade (any grade, grade 3-4, grade 5) presented by SOC/PT.

A by-subject AE listing will be provided. A by-subject listing of any AE requiring immune modulating medications will also be provided.

For those subjects treated in Arm B and for those intermediate/poor risk treated subjects in Arm A and Arm C:

The following analyses will be conducted using the 30 days safety window only:

- Overall summary of any AEs by worst CTC grade (1, 2, 3, 4, 5, not reported, total) presented by SOC/PT.
- Overall summary of any AEs that required immune modulating medication by worst CTC grade (any grade, grade 3-4, grade 5) presented by SOC/PT.
- Overall summary of drug-related AEs by worst CTC grade (1, 2, 3, 4, 5, not reported, total) presented by SOC/PT.

The following analyses will be conducted using the 30 days safety window and repeated using the 100 days safety window:

- Overall summary of drug-related AEs by worst CTC grade (any grade, grade 3-4, grade 5) presented by SOC/PT.

A by-subject AE listing will be provided. A by-subject listing of any AE requiring immune modulating medications will also be provided

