7.6.7 Immune-Mediated Adverse Events (US Submission)

IMAEs will be summarized by treatment group for each immune-mediated category / PT using the 100-day safety window:

- Overall summary of non-endocrine IMAEs by worst CTC grade (any grade, grade 3-4, grade 5) where immune modulating medication was initiated presented by Category / PT.
- Overall summary of endocrine IMAEs by worst CTC grade (any grade, grade 3-4, grade 5) presented by Category / PT.
- Overall summary of non-endocrine IMAEs leading to discontinuation by worst CTC grade (any grade, grade 3-4, grade 5) where immune modulating medication was initiated presented by Category / PT.
- Overall summary of endocrine IMAEs leading to discontinuation by worst CTC grade (any grade, grade 3-4, grade 5) presented by Category / PT.
- Overall summary of non-endocrine IMAEs leading to dose delay or reduction by worst CTC grade (any grade, grade 3-4, grade 5) where immune modulating medication was initiated presented by Category / PT
- Overall summary of endocrine IMAEs leading to dose delay or reduction by worst CTC grade (any grade, grade 3-4, grade 5) presented by Category / PT.
- Summaries of time-to onset and time-to resolution of non-endocrine IMAEs where immune modulating medication was initiated presented by Category.
- Summaries of time-to onset and time-to resolution of endocrine IMAEs presented by Category.

A by-subject listing of IMAEs will be provided. By-subject listings of time-to resolution for longest IMAEs cluster (any grade and grade 3-5 in separate summaries) will also be provided. For new studies which collect investigator assessment of potential IMAE data, a by-subject listing of AEs considered as immune-mediated events per investigator but not qualified for IMAEs definition will also be provided.

In addition, for all nivolumab treated subjects who experienced at least one IMAE, the following data presentation will be provided:

- Summary of subjects who were re-challenged with nivolumab by IMAE category, with extended follow-up
- Summary of subjects who were re-challenged with nivolumab or ipilimumab by IMAE category, with extended follow-up

For these, re-challenge is considered to have occurred when last nivolumab and/or ipilimumab infusion was administered after the onset of an IMAE.

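### Serious adverse events are summarised only to 30 days after last dose, although they are collected to 100 days; repeating the SAP 7.6.2 tables at 100 days would close a small reporting gap

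*SAP*

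**What the plan says.** **Collection.** Protocol 9.2.1 states: "All SAEs must be collected that occur during the screening period and within 100 days of the last dose of study treatment". The Schedule of Activities (Protocol Section 2) sets at least the same 100-day period for adverse events (AEs) in general.

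**Window rule.** SAP 6.1 leaves the choice to each analysis. For participants off study treatment, "AEs will be included if event occurred within a safety window of 30 days (or 100 days depending on the analysis"), counted from the last dose of study treatment.

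**SAE tables.** SAP 7.6.2 plans all-cause and drug-related SAE summaries by worst grade and states: "All analyses will be conducted using the 30-day safety window". No 100-day version is planned. A by-subject SAE listing for enrolled subjects is planned with no window stated.

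**Where the SAP does use 100 days.**
- Deaths with reasons, at 30 days, at 100 days and overall (7.6.1).
- Drug-related AEs by any grade, grade 3-4 and grade 5 (7.6.5): "The following analyses will be conducted using the 30 days safety window and repeated using the 100 days safety window".
- Immune-mediated AEs, or IMAEs (7.6.7): "IMAEs will be summarized by treatment group for each immune-mediated category / PT using the 100-day safety window". This set includes IMAEs leading to discontinuation.
- Other events of special interest, or OEOSI, both all-cause and drug-related (7.6.8).

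**The concern.** SAEs are named in the protocol's secondary safety endpoint, yet among the main safety outcomes they have no 100-day summary, and the SAP gives no reason. SAP 6.1 defines late-emergent drug-related AEs as those starting more than 100 days after the last dose. Days 31 to 100 therefore lie after the SAE tables end and before that category begins.

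At stake is the completeness of a descriptive safety summary. The trial is open-label (Protocol 7.3), and whether an event is drug-related is a physician's judgment (Protocol Appendix 3). An all-cause SAE table does not depend on that judgment. The general 100-day AE table that the SAP does plan depends on it.

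**Working it through.** The plan states no figure here that could be reproduced. The check is a comparison of windows, followed by simple arithmetic.

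**Step 1. Days not covered.** Collection runs 100 days after last dose and the SAE tables run 30. 100 - 30 = 70 days, or 70% of the post-dose collection period. The on-treatment period is fully covered under either window, so 70% is a share of follow-up days and not a share of SAEs.

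**Step 2. Where an SAE starting on days 31 to 100 is summarised.**
- Fatal: in the 100-day death summary (7.6.1).
- Drug-related: in the 100-day drug-related AE table (7.6.5), by grade, with no seriousness flag.
- IMAE: in the 100-day IMAE tables (7.6.7), with no seriousness flag. Under SAP 7.1.1.3, non-endocrine events must have been treated with immune-modulating medication. Events with a clear alternative cause are left out unless they have an immune-mediated component.
- OEOSI: in the 100-day OEOSI tables (7.6.8), with no seriousness flag, and only for listed preferred terms.
- Non-fatal and none of these: in no visible summary table, only in the listing.

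The other candidates do not fill the gap. The serious select AE tables (7.6.6.1) and the exposure-adjusted rates (7.6.9) also stop at 30 days. No visible table labelled as serious runs past day 30. Parts of the SAP are redacted, but 7.6.2 is legible in full.

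**Step 3. Is 30 days short for the longest-acting drug?** This is supplementary. The contraception rules in Protocol 6.1 are a fixed number of days "plus the time required for the investigational drug to undergo approximately five half-lives". Taking that drug to be nivolumab (an assumption) and a month as 30 to 30.4375 days:
- Women, 5 months less 30 days: (5 x 30 - 30)/5 = 24.0 days; (5 x 30.4375 - 30)/5 = 24.4 days.
- Men, 7 months less 90 days: (7 x 30 - 90)/5 = 24.0 days; (7 x 30.4375 - 90)/5 = 24.6 days.
- Fraction remaining, 2^(-t/half-life): at day 30, 0.42 to 0.43; at day 100, about 0.06.

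**Step 4. Illustration on assumed hazards.** Of first events in days 1 to 100 after last dose, the share caught by day 30 would be:
- Constant hazard, 100-day risk p: (1 - (1 - p)^0.3)/p, which is 0.301 at p = 0.01 and 0.324 at p = 0.20.
- Hazard proportional to remaining drug: (1 - 0.420)/(1 - 0.056) = 0.61.

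Neither hazard shape comes from the documents. These shares show only that the later window could hold a material part of post-dose events; they do not estimate a count.

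**The case against.** **No rule is broken.** SAP 6.1 allows either window, Protocol 10.3.2 sets none for SAE tables, and collecting to day 100 does not oblige every table to run that far. This stands. The point is a reporting improvement and not an error.

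**Limiting all-cause tables to 30 days is defensible.** Later events may arise on subsequent therapy. This stands as a reason to keep 30 days as the main display. It does not justify having no 100-day version, and it does not explain why the drug-related SAE table stops at 30 days when drug-related AEs are repeated at 100.

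**A reader might infer that late immune-mediated toxicity in Arm A is hidden, so that the comparison favours Arm A.** The documents do not support this.
- Drug-related AEs, IMAEs, OEOSI and deaths are all summarised to 100 days.
- The window runs from the last dose of study treatment. Cabozantinib may continue after nivolumab stops (Protocol 5.1), and events in that period are still on-treatment. The residual-drug figures apply only where nivolumab is given up to the end of all treatment.
- Arm C is cut at day 30 as well.
- The protocol's safety objective is to assess safety and tolerability; no formal SAE comparison is planned.

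**A reader might extend the point to AEs leading to discontinuation,** because SAP 7.6.3 says "The analyses will be conducted using the 30-day safety window". This adds little. IMAEs leading to discontinuation are already tabulated to 100 days in 7.6.7, and an event that ends treatment normally begins before or near the last dose. The exception is an event arising more than 30 days into a hold of all study drugs.

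**Conclusion.** The point holds as a low-cost improvement to safety reporting. Two gaps remain for days 31 to 100 after last dose: non-fatal SAEs outside the drug-related, IMAE and OEOSI categories are in no visible summary table, and late drug-related SAEs are counted without being identified as serious.

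The gap applies to both arms. It matters most for participants who stop all study drugs together, as Protocol 8.1.1 provides for Arms A and B when toxicity is related to all the drugs or its cause cannot be determined. Its extent is 70 of 100 post-dose collection days. The number of events and the direction of any between-arm difference cannot be derived from the documents.

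This conclusion rests on the visible text of the SAP and does not depend on the half-life inference. Alpha, power and the primary analysis are unaffected.

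**What to change.** In SAP 7.6.2, replace the window sentence with wording to this effect: *The all-cause and drug-related SAE summaries will be produced with the 30-day safety window and repeated with the 100-day safety window. The 30-day tables are the main display. The 100-day tables will carry a note that days 31 to 100 may include events arising on subsequent therapy.* SAP 7.6.5 already uses this arrangement for drug-related AEs. No change to 7.6.3 is needed.

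The cost is a few repeat tables from existing programs, with no new data collection. The one drawback is that later events may reflect subsequent therapy; showing both windows with the note deals with it.

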7.6.3 Adverse Events Leading to Discontinuation of Study Therapy

AEs leading to discontinuation will be summarized by treatment group:

- Overall summary of AEs leading to discontinuation by worst CTC grade (any grade, grade 3-4, grade 5) presented by SOC/PT.
- Overall summary of drug-related AEs leading to discontinuation by worst CTC grade (any grade, grade 3-4, grade 5) presented by SOC/PT.

The analyses will be conducted using the 30-day safety window.

A by-subject AEs leading to discontinuation listing will be provided.

Note that for all intermediate/poor risk treated subjects in Arm A and Arm C, AEs leading to discontinuation will be summarized by treatment group.

Similar table will be presented for those subjects treated in Arm B.

Note that

- for Arm A, AEs leading to discontinuation from cabozantinib only, nivolumab only, and both cabozantinib and nivolumab.
- for Arm B, AEs leading to discontinuation from cabozantinib only, nivolumab and ipilimumab only, and from cabozantinib, nivolumab, and ipilimumab will be summarized in all the tables specified in this section.

